5.4.2 Concomitant Antibacterial Medications

Concomitant systemic antibacterials are prohibited during the study, up to the TOC visit, unless it has been determined that the antibacterial would not have a potential effect on outcome evaluations in patients with uUTI.

5.4.3 Non-drug Adjunctive Therapy

None allowed

6 STUDY PROCEDURES

6.1 Screening (Day 1)

If a patient is presenting with uUTI symptoms and has a positive dipstick for leukocyte esterase AND nitrite, and all other Inclusion and no Exclusion criteria are met then the Investigator (or an appropriate delegate at the Investigator site) will obtain written informed consent from each patient prior to the initiation of any study related activities.

The following procedures will be performed prior to ciprofloxacin administration:

- Demographics and medical history
- Temperature reading
- Collect Height and Weight
- Collect urine for dipstick analysis. If done at an outside institution, then repeat testing.
- Review previous drug and non-drug treatments (defined as within the past 30 days) and concomitant drug treatments
- Adverse events occurring after signing of ICF
- Administer and collect patient assessment questionnaire from patient (Appendix 3)

6.2 Treatment Period

6.2.1 Baseline (Day 1)

The following activities will be completed:

• Collect urine for urinalysis, and urine culture and sensitivity

Clinical Trial Protocol: IT-004-401

- Issue prescription of generic ciprofloxacin
- Check and document compliance with study medication (phone call)
- Distribute patient dosing diary

6.2.2 End Of Treatment (EOT) Day 3 or 4 (+1 day)

- Collect urine for culture and sensitivity
- Review concomitant medications
- Check and document compliance with study medication
- Collect patient dosing diary
- Assess symptoms by spontaneous reporting of adverse events and by asking the subjects to respond to a non-leading question such as "How do you feel?
- Administer and collect patient assessment questionnaire from patient (Appendix 3)
- Investigator-Determined Assessment of Clinical Response (Section 7.2.3)

6.3 Follow-up Period

6.3.1 Test of Cure (TOC) Day 12 (+/- 1 day)

- Collect urine for culture and sensitivity
- Review concomitant medications
- Assess symptoms by spontaneous reporting of adverse events and by asking the subjects to respond to a non-leading question such as "How do you feel?
- Administer and collect patient assessment questionnaire from patient (Appendix 3)
- Investigator-Determined Assessment of Clinical Response (Section 7.2.3)

6.3.2 Post Test of Cure (TOC) Day 21 (+/- 3 days)

Call patient to assess for resolution of uUTI symptoms

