6.4 Patient Withdrawal from Treatment or Study

Patients may withdraw from the study or ciprofloxacin at any time at their own request, or they may be withdrawn at any time at the discretion of the Investigator or Iterum Therapeutics for safety, behavioral, or administrative reasons.

If a patient does not return for a scheduled visit, every effort should be made to contact the patient. In any circumstance, every effort should be made to document patient outcome, if possible. If the patient withdraws or is withdrawn from ciprofloxacin treatment, the Investigator should inquire about the reason for withdrawal, request the patient to return for all protocol-specified assessments, if possible, and follow-up with the patient regarding any unresolved AEs through the TOC.

If the patient withdraws from the study, and also withdraws consent for disclosure of future information, no further study-specific evaluations should be performed, and no additional data should be collected. Iterum Therapeutics may retain and continue to use any data collected before such withdrawal of consent.

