8 ADVERSE EVENT REPORTING

8.1 Adverse Events

All observed or volunteered AEs, regardless of suspected causal relationship, will be reported as described in the following sections.

For all AEs, the Investigator must pursue and obtain adequate information both to determine the outcome of the AE and to assess whether it meets the criteria for classification as a serious AE (SAE) requiring immediate notification to Iterum Therapeutics. For all AEs, sufficient information should be obtained by the Investigator to determine the causality of the AE. The Investigator is required to assess causality. All AEs will be followed-up by the Investigator until the event or its sequelae resolve or stabilize at a level acceptable to the Investigator, and Iterum concurs with that assessment.

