8.2 Reporting Period

Adverse events will be collected from the time that the patient provides informed consent through TOC.

For SAEs, the reporting period to Iterum Therapeutics begins from the time that the patient signed informed consent, which may be prior to the patient's participation in the study, i.e., prior to undergoing any study-related procedure through the TOC. Any SAE occurring any time after the reporting period must be promptly reported if a causal relationship to investigational product is suspected

All AEs should be recorded on the CRF if they occur from the time the patient provides informed consent through TOC.

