13 DEFINITION OF END OF STUDY

13.1 End of Study in Participating Countries

End of Study in all participating countries is defined as the TOC Visit.

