Appendix 4 Ciprofloxacin Tablets – USPI

HIGHLIGHTS OF PRESCRIBING INFORMATION

These highlights do not include all the information needed to use CIPRO safely and effectively. See full prescribing information for CIPRO.

CIPRO® (ciprofloxacin hydrochloride) tablet, for oral use

CIPRO® (ciprofloxacin hydrochloride), for oral suspension

Initial U.S. Approval: 1987

WARNING: SERIOUS ADVERSE REACTIONS INCLUDING TENDINITIS, TENDON RUPTURE, PERIPHERAL NEUROPATHY, CENTRAL NERVOUS SYSTEM EFFECTS AND EXACERBATION OF MYASTHENIA GRAVIS

See full prescribing information for complete boxed warning.

- Fluoroquinolones, including CIPRO*, have been associated with disabling and potentially irreversible serious adverse reactions that have occurred together (5.1), including:
- Tendinitis and tendon rupture (5.2) Peripheral neuropathy (5.3)
- o Central nervous system effects (5.4)

Discontinue CIPRO immediately and avoid the use of fluoroquinolones, including CIPRO, in patients who experience any of these serious adverse reactions (5.1)

- Fluoroquinolones, including CIPRO, may exacerbate muscle weakness in patients with myasthenia gravis. Avoid CIPRO in patients with known history of myasthenia gravis. (5.5)
- Because fluoroquinolones, including CIPRO, have been associated with serious adverse reactions (5.1-5.15), reserve CIPRO for use in patients who have no alternative treatment options for the following indications:

 Acute exacerbation of chronic bronchitis
 O Acute uncomplicated cystitis (1.11)
 Acute sinusitis (1.12)

----- RECENT MAJOR CHANGES -----

--- INDICATIONS AND USAGE -----

Boxed Warning	M/2016 Indications and Usage (1.10, 1.11, 1.	2) M/2016 Dosage and Administration, Dosage in Adults (2.1) M/201
Warnings and Pred	eautions (5.1)	M/2016

CIPRO is a fluoroquinolone antibacterial indicated in adults (≥18 years of age) with the following infections caused by designated, susceptible bacteria and in pediatric patients where indicated: • Skin and Skin Structure Infections (1.1)

- Bone and Joint Infections (1.2)
- Complicated Intra-Abdominal Infections (1.3)
- Infectious Diarrhea (1.4)
- Typhoid Fever (Enteric Fever) (1.5)
- Uncomplicated Cervical and Urethral Gonorrhea (1.6)
- Inhalational Anthrax post-exposure in adult and pediatric patients (1.7)
- Plague in adult and pediatric patients (1.8)
- Chronic Bacterial Prostatitis (1.9)
- Lower Respiratory Tract Infections (1.10)

 Acute Exacerbation of Chronic Bronchitis

every 12 hours

single dose

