7.8 Safety Analyses

Safety analysis will be conducted in the safety population. Safety parameters include adverse events.

Verbatim descriptions of AEs will be coded using Version 21.0 or higher of MedDRA. Summary tables will be provided for all treatment-emergent AEs (TEAEs). An AE is defined as any untoward medical occurrence in a clinical investigation patient administered a product or medical device, unless the event is captured in the study endpoint, as defined below; the event need not necessarily have a causal relationship with the treatment or usage. ATEAE is any AE that newly appeared, increased in frequency, or worsened in severity following initiation of ciprofloxacin. In addition, all AEs (including non-TEAEs), serious TEAEs, and TEAEs leading to study drug discontinuation will be provided in listings containing patient number, verbatim term, MedDRA system organ class and preferred terms, seriousness flag, intensity, relationship to study drug, action taken and outcome.

An overall summary of AEs will include number of patients who experienced at least one AE of the following categories: any AE, any TEAE, any drug-related TEAE defined as possibly or probably related to study drug, any serious TEAE, any drug- related SAE, any SAE leading to death, any TEAE leading to premature discontinuation of study drug, and any SAE leading to premature study drug discontinuation.

The number and percentage of patients reporting a TEAE will be tabulated by system organ class and preferred term for all TEAEs and TEAEs through TOC. TEAEs through TOC will also be summarized separately by system organ class, preferred term, and intensity (mild, moderate, and severe); and by system organ class, preferred term, and relationship (unrelated or related to study drug). A table will provide all SAEs (through TOC) by system organ class and preferred term. For all analyses of TEAEs, if the same AE (based on preferred term) is reported for the same patient more than once, the AE is counted only once for that preferred term and at the highest intensity and strongest relationship to study drug.

Analysis of the distribution of the duration of each adverse event as well as an overall mean adverse event duration will be presented.

If an AE starts on the same day that dosing is initiated, and the start time of the AE is missing then the AE is considered TEAE.

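### The Day 21 call asks only about UTI symptoms while adverse-event collection stops at TOC, so later events are not actively sought and the SAP's overall TEAE table has no systematic data beyond TOC

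*Protocol*

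**What the plan says.** - **Day 21 contact.** Protocol 6.3.2 gives it one task: "Call patient to assess for resolution of uUTI symptoms". The EOT and TOC visits (6.2.2, 6.3.1) each carry an open question about how the patient feels; the call has none listed. Both Schedules (Protocol Appendix 1, SAP Appendix 1) mark adverse events at screening, EOT and TOC, but not at Day 21.
- **AE period.** Protocol 8.2: "Adverse events will be collected from the time that the patient provides informed consent through TOC". On recording, the same section says: "All AEs should be recorded on the CRF if they occur from the time the patient provides informed consent through TOC". Section 8.11 ends elicitation at the same point.
- **End of study.** Protocol 13.1: "End of Study in all participating countries is defined as the TOC Visit". That is before the last scheduled contact.
- **Safety tables.** SAP 7.8 counts patients by system organ class and preferred term "for all TEAEs and TEAEs through TOC".
- **Follow-up of open events.** Protocol 8.1: "All AEs will be followed-up by the Investigator until the event or its sequelae resolve or stabilize". Protocol 6.4, for patients withdrawn from ciprofloxacin: "follow-up with the patient regarding any unresolved AEs through the TOC".
- **Synopsis.** It has AEs collected at each visit, without naming TOC as the end. SAP 6.3 lists Day 21 in its table of visit windows.

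**The concern.** Safety is reported only as summaries of AEs (Protocol 9.6), and Protocol 7.1.1 adds no laboratory tests beyond routine urine testing. What the AE tables contain therefore depends on when somebody asks. The plan pays for a further contact about nine days after TOC and does not use it for safety.

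Two things are at stake. First, the AE record closes 7 to 10 days after the last dose of a drug whose appended label says that fluoroquinolones "have been associated with disabling and potentially irreversible serious adverse reactions that have occurred together". Second, a reader of the study report who sees an overall TEAE table next to one cut at TOC could take the first as evidence of longer surveillance, when no systematic data would lie behind the difference.

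**Working it through.** The documents give no figure that depends on this point, so there is none to reproduce. The check is day arithmetic and a comparison of the reporting rules.

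**Inputs.** TOC is Day 12 ±1, so Day 11–13 (6.3.1). The call is Day 21 ±3, so Day 18–24 (6.3.2). The last scheduled dose is on Day 3, or on Day 4 after an evening first dose (3.1). 250 women are to be treated (9.1).

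**Length of observation**

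| Interval | Minimum | Nominal | Maximum |
|---|---|---|---|
| Last dose to TOC | 11 − 4 = 7 | 12 − 4 = 8 or 12 − 3 = 9 | 13 − 3 = 10 |
| TOC to call | 18 − 13 = 5 | 21 − 12 = 9 | 24 − 11 = 13 |
| Last dose to call | 18 − 4 = 14 | 21 − 4 = 17 or 21 − 3 = 18 | 24 − 3 = 21 |

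Using the call would roughly double nominal post-dose observation. At present 9 of the 21 nominal days (43%) have no systematic AE collection.

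**What happens to an event after TOC**

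| Event | Governing text | Result |
|---|---|---|
| New non-serious AE | 8.2 and 8.11 stop at TOC | Outside collection |
| New SAE judged unrelated | 8.2 requires a suspected causal link after the period | Outside collection |
| New SAE, related or of unknown cause | 8.2 has no end date for suspected-related SAEs; 8.8 handles unknown as related | Reportable if the site hears of it |
| AE open at TOC | 8.1 | Followed until resolved or stable, but 6.4 stops at TOC for women withdrawn from drug |
| Pregnancy | 8.9 is triggered during the study, which 13.1 ends at TOC; 8.12.1 runs 24 hours from awareness with no end date | Reportable once known and followed to outcome; no step asks after TOC |

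**The two TEAE tables.** The overall table can differ from the through-TOC table only by events that start after TOC and reach the database. Those are spontaneous reports, chiefly suspected-related SAEs.

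**Scale.** The documents give no rate for late events, so the rate p is assumed. If all 250 women were reached, the chance that at least one has an event in the added window is 1 − (1 − p)^250:

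- p = 0.2%: 39%
- p = 0.5%: 71%
- p = 1%: 92%
- p = 2%: 99%

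If all were asked and none reported an event, the one-sided 95% upper bound would be 1 − 0.05^(1/250) = 1.2%. The current plan has no post-TOC denominator from which to make such a statement.

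**The case against.** **The TOC cut-off looks deliberate.** It recurs in AE collection, elicitation, concomitant-medication recording (5.4.1), contraception (4.4) and both Schedules. The drug is marketed, given for three days at the dose in its appended label, and followed for 7–10 days afterwards. No document sets a longer standard. This stands: ending collection at TOC is not an error in itself. It does not explain the second TEAE table or an End of Study that precedes a scheduled contact.

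**Late events are not simply lost.** A reader might infer that events and pregnancies after TOC are missed altogether. The documents do not support that, given the late-SAE rule in 8.2, the handling of unknown causality in 8.8, follow-up under 8.1, and pregnancy reporting under 8.9 and 8.12.1. The text supports no more than that they are not actively sought.

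**The call may still pick up infectious complications.** A symptom question, with the Day 21 clinical response in SAP 5.3, could reveal progression of the infection. That stands in part. Such a case could appear in the efficacy data, but an admission judged unrelated to the drug would still be absent from the AE tables, and the symptom question does not reach events unconnected with the urinary tract.

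**Sections 6.4 and 8.1 can be read together**, with 6.4 as the minimum contact after withdrawal from drug. That is a fair reading, but a site should not have to choose it. Nor do the documents show that women withdrawn from drug are those most likely to have had a drug reaction: 6.4 also covers the patient's own request and behavioral or administrative reasons.

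**Conclusion.** The point holds as a cheap improvement to safety ascertainment plus a set of texts to reconcile. New non-serious AEs and SAEs judged unrelated that begin after TOC are outside collection, pregnancy is not asked about, and the overall TEAE table has no systematic source beyond TOC. The measurable size is the window: 9 nominal days (range 5–13) between TOC and the call. The number of events it would yield is unknown; the probabilities above rest on assumed rates and on all 250 women being reached.

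Three further inferences should not be drawn. The call cannot be said to reach every woman, because Amendment 02 introduced it and the documents do not say how many had already finished. No reason is given for limiting it to symptoms, so the AE cut-off cannot be named as the cause. The documents also give no time to recognition of pregnancy, so nothing supports a claim that a conception during dosing would be known by the call.

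The study is descriptive, with no hypothesis test (SAP 7.6), and the primary endpoint at TOC is untouched.

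**What to change.** **Preferred.**

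- Add four items to the Day 21 call in 6.3.2: a non-leading AE question, the status of any AE open at TOC, any hospital admission, and any pregnancy.
- Extend 8.2, 8.11 and the AE row of both Schedules to the Day 21 contact.
- Set End of Study in 13.1 to that contact.

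The two SAP 7.8 tables would then have distinct data behind them.

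**If collection is kept at TOC.** Drop the overall TEAE table, or footnote its post-TOC entries as spontaneous reports.

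**In either case.** Reconcile 6.4 with 8.1 on how long unresolved AEs are followed, and the synopsis wording on AE collection at each visit with 8.2.

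The cost is protocol and SAP wording and a few minutes on a call already scheduled. The downside is a few more AE records, taken by telephone without an examination.

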6.4 Patient Withdrawal from Treatment or Study

Patients may withdraw from the study or ciprofloxacin at any time at their own request, or they may be withdrawn at any time at the discretion of the Investigator or Iterum Therapeutics for safety, behavioral, or administrative reasons.

If a patient does not return for a scheduled visit, every effort should be made to contact the patient. In any circumstance, every effort should be made to document patient outcome, if possible. If the patient withdraws or is withdrawn from ciprofloxacin treatment, the Investigator should inquire about the reason for withdrawal, request the patient to return for all protocol-specified assessments, if possible, and follow-up with the patient regarding any unresolved AEs through the TOC.

If the patient withdraws from the study, and also withdraws consent for disclosure of future information, no further study-specific evaluations should be performed, and no additional data should be collected. Iterum Therapeutics may retain and continue to use any data collected before such withdrawal of consent.

7 ASSESSMENTS

7.1 Safety

7.1.1 Clinical Laboratory Assays

No additional laboratory testing will be performed beyond routine urine testing for uUTI.

7.2 Efficacy

7.2.1 Overall Response

Overall Response is assessed on Day 12 (+/- 1 day) TOC using the definitions listed below:

A patient will be defined as a responder if the following criteria are met (programmatically, based on the data on the CRF):

- The patient is alive
- The patient has received no rescue therapy for uUTI
 - If an antibiotic active against the urinary tract pathogen is given for other reasons, then the patient will be considered indeterminate, and analyzed as a non-responder for uUTI
- The patient has resolution of the symptoms of uUTI present at trial entry and no new uUTI symptoms
- Urine culture taken on Day 12 (+/- 1 day) demonstrates <10³ CFU/mL of the baseline uropathogen

All other patients will be considered non-responders. If data are unavailable to determine if the patient is a responder or non-responder, the patient will be considered as having an indeterminate response.

7.2.2 Microbiologic

Microbiologic Response is assessed on Day 3 or 4 (+1 day) EOT and Day 12 (+/- 1 day) TOC using the definitions listed below:

Microbiological response	Definition
Eradication	A urine culture taken at baseline and compared with the culture from the EOT visit or TOC visit showed that the urine culture obtained at the relevant visit demonstrated <10 ³ CFU/mL of the original uropathogen.
Persistence	A uropathogen present at baseline grew at $\geq 10^3$ CFU/mL at the time-point of analysis, i.e. EOT or TOC.
Indeterminate	Patient was lost to follow-up or an assessment was not undertaken such that no urine culture was obtained (or culture results could not be interpreted for any reason) at either the EOT or the TOC visit.

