The number and percentage of patients with a microbiologic success at the Day 12 (+/-1 day) visit will be determined. The validity of the urine dipstick as a screening tool to identify patients with a positive urine culture will be evaluated by calculating the percentage of patients with both a positive nitrite test and a positive test for pyuria on dipstick/urinalysis, who have $\geq 10^5$ CFU/ml of a uropathogen isolated from urine culture. Safety analyses will be conducted in all patients who receive any amount of ciprofloxacin. Safety will be assessed through summaries of AEs.

Date of Original Approved Protocol: September 29, 2017

Date of Most Recent Protocol Amendment (if applicable): March 27, 2018

TABLE OF CONTENTS

SYN	NOPSIS	2
LIST	T OF APPENDICES	13
LIST	T OF ABBREVIATIONS AND DEFINITIONS OF TERMS	14
1	INTRODUCTION	17
1	1.1 Indication	17
1	1.2 Background and Rationale	17
	1.2.1 Rationale for Study	17
	1.2.2 Dose Rationale	18
2	STUDY OBJECTIVES	18
2	2.1 Objectives	18
3	STUDY DESIGN	19
3	3.1 Investigational Study Medications	19
3	3.2 Adjunctive Systemic Antibiotics	19
3	3.3 Additional, Non-Study Therapy Antibiotics	20
4	STUDY POPULATION SELECTION	20
4	4.1 Inclusion Criteria	20
4	4.2 Exclusion Criteria	21
4	4.3 Enrollment Criteria	22
4	4.4 Women of Child-Bearing Potential	22
5	STUDY TREATMENTS	23
5	5.1 Allocation to Treatment	23
5	5.2 Drug Supplies	23
	5.2.1 Formulation and Packaging	23

	5.2.2	Preparation and Dispensing	24
	5.2.3	Compliance	24
	5.3 Dr	ug Storage and Drug Accountability	24
	5.4 Me	edication(s), Adjunctive Therapy and Non-drug Therapy	25
	5.4.1	Concomitant Medications	25
	5.4.2	Concomitant Antibacterial Medications	25
	5.4.3	Non-drug Adjunctive Therapy	25
6	STUDY	PROCEDURES	26
	6.1 Sci	reening (Day 1)	26
	6.2 Tre	eatment Period	26
	6.2.1	Baseline (Day 1)	26
	6.2.2	End Of Treatment (EOT) Day 3 or 4 (+1 day)	27
	6.3 Fo	llow-up Period	27
	6.3.1	Test of Cure (TOC) Day 12 (+/- 1 day)	27
	6.3.2	Post Test of Cure (TOC) Day 21 (+/- 3 days)	28
	6.4 Pat	tient Withdrawal from Treatment or Study	28
7	ASSESS	MENTS	28
	7.1 Sa	fety	28
	7.1.1	Clinical Laboratory Assays	28
	7.2 Eff	ficacy	29
	7.2.1	Overall Response	29
	7.2.2	Microbiologic	29
	7.2.3	Investigator-Determined Clinical Response	30
	7.2.4	Other Assessments	31

8	ADV	ERSE EVENT REPORTING	31
	8.1	Adverse Events	31
	8.2	Reporting Period.	31
	8.3	Definition of an AE	32
	8.4	Abnormal Test Findings	33
	8.5	SAEs	33
	8.6	Hospitalization	34
	8.7	Severity Assessment	35

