4.5 Clinically Evaluable (CE)

Clinically evaluable is defined both at the end of treatment (EOT) and test of cure (TOC) visits.

- All patients who were included in the MITT population and meet the following criteria are clinically evaluable.
 - a) Received a minimum of four doses of ciprofloxacin.
 - b) Had no important protocol deviations that would affect the assessment of efficacy as indicated in the protocol deviation log (see section 7.9). These will be pointed out by clinical team and marked in the CE spreadsheet.
 - c) Had a Clinical response assessment of clinical cure or clinical failure (and not indeterminate) at the EOT or TOC visits (within Protocol visit window), respectively.
 Note: Since the PSAQ does not contain a date completed, the date if lab culture will be used.
 - d) Did not receive any antibiotic therapy with potential activity against any of the baseline uropathogens collected at screening between the time of the baseline culture and the EOT or TOC culture, respectively. This excludes the protocol defined study therapy and patients who were considered clinical failures and required additional antibiotic therapy. Patients with a coinfection with a gram-positive uropathogen resistant to ciprofloxacin are allowed to receive agents with narrow spectrum gram-positive coverage (i.e., such as linezolid or vancomycin).

Note: This rule will be applied through the manual review of CE spreadsheet by the sponsor.

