5.3 Additional Efficacy Outcomes Measures

Microbiologic response

Microbiologic response is assessed on Day 3 or 4 (+1 day) EOT and Day 12 (+/- 1 day) TOC in the ITT, m-MITT, CE-EOT, CE-TOC, ME-EOT and ME-TOC populations.

Microbiological	Definition
response	
Eradication	A urine culture taken at baseline and compared with the culture
	from the Day 3 (+1 day) (EOT) visit or Day 12 (+/- 1 day)
	(TOC) visit showed that the urine culture obtained at the
	relevant visit demonstrated <10 ³ CFU/mL of the original
	uropathogen.
Persistence	Uropathogen present at baseline grew at ≥10 ³ CFU/mL at the
	time-point of analysis, i.e. EOT or TOC.
Indeterminate	Patient was lost to follow-up or an assessment was not
	undertaken such that no urine culture was obtained (or culture
	results could not be interpreted for any reason) at either the
	EOT or the TOC visit.

• Clinical response:

Clinical response (done programmatically) will use the definitions below to document response at Day 3 or Day 4 (+ 1 day) (EOT), Day 12 (+/- 1 day) (TOC) and Day 21 in the ITT, m-MITT, CE-EOT, CE-TOC, ME-EOT and ME-TOC populations.

Clinical response	Definition
Clinical cure	All pre-therapy signs and symptoms of the index infection had resolved such that no additional antibiotics were required
Clinical failure	Patients who met any one of the criteria below were considered as failure:
	Death related to uUTI prior to Day 3 or Day 12 or Day 21 respectively
	No apparent response to treatment; persistence or progression of most or all pre-therapy signs and symptoms or use of additional antibiotics for the current infection
	Patient previously met criteria for failure and received rescue antibiotics
Indeterminate	Study data were not available for evaluation of efficacy for any reason, including:
	Patient lost to follow-up or assessment not undertaken such that a determination of clinical response could not be made at either the EOT or TOC visit
	Death prior to Day 3 or Day 12 or Day 21, respectively, where uUTI was clearly noncontributory

In addition to the clinical response above, following sensitivity analyses will be performed on Day 12 (+/- 1 day) in the m-MITT population,

- Sensitivity Analysis 1: Will follow the same definition of clinical response defined in section 5.3 except, urgency is excluded and considering all other symptoms are resolved and no new uUTI symptoms.

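### Microbiologic response has no rescue rule, so a Day 12 culture cleared after a rescue antibiotic is scored as a ciprofloxacin eradication in m-MITT and in ME-TOC

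*Protocol*

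**What the plan says.** **Microbiologic response.** Protocol 7.2.2 bases all three categories on the visit culture.
- Eradication: the comparison with baseline "showed that the urine culture obtained at the relevant visit demonstrated" under 10^3 CFU/mL of the original organism.
- Persistence: "A uropathogen present at baseline grew at" 10^3 CFU/mL or more.
- Indeterminate: no culture was obtained, "or culture results could not be interpreted for any reason".

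The SAP 5.3 table has the same structure ("showed that the urine culture obtained at the" visit for eradication; "Uropathogen present at baseline grew at" the same threshold for persistence). Other antibiotics appear in none of the categories.

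**Other efficacy outcomes.** Overall response (Protocol 7.2.1, SAP 5.1) requires that "The patient has received no rescue therapy for uUTI". Clinical response (Protocol 7.2.3, SAP 5.3) makes additional antibiotics for the current infection a failure.

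**Populations.** m-MITT depends only on dosing and the baseline culture (SAP 4.4). The CE rule against other active antibiotics (Protocol 9.2, CE item e; SAP 4.5, item d) carries an exemption: "This excludes the protocol defined study therapy and patients who were considered clinical failures and required additional antibiotic therapy". ME is built from m-MITT and CE, and needs an eradication or persistence result (SAP 4.6).

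**Reporting.** The Protocol Synopsis states: "The number and percentage of patients with a microbiologic success at the Day 12 (+/-1 day) visit will be determined". SAP 5.3 reports microbiologic response at EOT and TOC across six named populations, and by key pathogen and baseline ESBL status in m-MITT and ME.

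**The concern.** A negative culture on Day 12 says that the organism is gone. It does not say which drug removed it. Overall and clinical response deal with this by counting rescue as failure; microbiologic response is the one efficacy outcome left without a rule.

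The error runs one way, since it can only add eradications to ciprofloxacin's count. It matters most where rescue is most likely, which is plausibly the non-susceptible infections. Resistance excludes a woman only if her culture result is available at entry (Protocol 4.2, item 10), so a susceptibility result can arrive after dosing has started. The study rationale (Protocol 1.2.1) asks how often patients with fluoroquinolone-resistant pathogens respond clinically or bacteriologically. A rate that includes another drug's clearances does not answer that. In a single-arm descriptive study the reported percentages are the result, and no comparator offsets the error.

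**Working it through.** **Step 1: follow one patient through the rules.** Take a woman in m-MITT with at least four doses. She fails ciprofloxacin, starts another antibiotic for the uUTI after EOT, and has an in-window Day 12 culture below 10^3 CFU/mL.
- Overall response: non-responder, because of rescue (SAP 5.1).
- Clinical response: failure, because of additional antibiotics (SAP 5.3).
- Microbiologic response: eradication, because only the culture is read (SAP 5.3).
- m-MITT: stays in, since membership is fixed at baseline (SAP 4.4).
- CE-TOC: stays in. Failure is an allowed assessment under SAP 4.5 item c, and item d exempts her antibiotic.
- ME-TOC: stays in. Her culture is interpretable and scored as eradication (SAP 4.6).

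**Step 2: look for a repair elsewhere.** SAP 6.5 makes an outcome indeterminate only for missing data, and nothing is missing here. SAP 7.4 reports how many patients took an active antibiotic before the EOT or TOC culture, but does not change their scoring. SAP Section 8 lists no change on this point.

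**Step 3: size.** Inputs from Protocol 9.1 and SAP 6.1: 250 enrolled, 50 expected without a qualifying culture, 40 expected non-susceptible. No formula lies behind the 250, so there is no plan figure to reproduce.
- Expected m-MITT: 250 − 50 = 200. Susceptible, if all 40 non-susceptible women are in m-MITT: 200 − 40 = 160.
- One misattributed eradication: 1/200 = 0.5 points overall; 1/40 = 2.5 points in the non-susceptible group.
- In general, inflation = (share rescued before the Day 12 culture) × (share of those clear at Day 12), assuming that none had cleared before rescue and all return for the culture.

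The documents give neither share. Assumed values:

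| Rescued | 80% clear | 95% clear |
|---|---|---|
| 5% | 4.0 points | 4.8 points |
| 10% | 8.0 | 9.5 |
| 20% | 16.0 | 19.0 |
| 30% | 24.0 | 28.5 |
| 40% | 32.0 | 38.0 |

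As rescue approaches 0%, so does the inflation. The figures apply to whichever group has those rates. If only the 40 non-susceptible women were rescued, the ends of the table give 40 × 0.05 × 0.80 = 1.6 women (1.6/200 = 0.8 points overall) and 40 × 0.40 × 0.95 = 15.2 women (15.2/200 = 7.6 points overall).

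**Step 4: an assumed example by susceptibility.**
- Non-susceptible, n = 40: 16 clear without rescue, 12 are rescued of whom 10 clear, 12 persist. As written: 26/40 = 65% (Wilson 95% CI 49.5 to 77.9). Rescued women not counted: 16/40 = 40% (26.3 to 55.4).
- Susceptible, n = 160: 140 clear without rescue, 8 are rescued of whom 7 clear. As written: 147/160 = 91.9%. Rescued women not counted: 140/160 = 87.5%.
- Difference between groups: 91.9 − 65 = 26.9 points as written, against 87.5 − 40 = 47.5 points.

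If rescue is commoner in non-susceptible infections, the plan as written understates the contrast by susceptibility.

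**The case against.** **The primary result.** A reader might infer that the primary endpoint is biased, because the primary objective names microbiologic response. The documents do not support that. The primary outcome is overall response at Day 12 in m-MITT, which already makes a rescued patient a non-responder. Microbiologic response alone is an additional outcome (Protocol 9.5.3, SAP 5.3), called secondary in Protocol 9.7, and it is descriptive with no test attached. This objection stands.

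**Size in the non-susceptible group.** Assuming 20 to 50% rescued and 80 to 90% cleared, a reader might infer a firm inflation of 16 to 45 points. The documents give no such rates. Some patients respond despite in vitro resistance, as Protocol 1.2.1 itself says, so some may have cleared before rescue; others may miss the Day 12 culture and become indeterminate. The lower end must therefore be near 0. The analysis by susceptibility in Protocol 9.5.1.1 concerns the primary outcome. SAP 5.3 breaks microbiologic response down by pathogen and ESBL, and only the general wording in the Synopsis and Protocol 9.3 extends to a split by susceptibility.

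**Reach.** The six populations span two visits. Two of them, CE-EOT and ME-EOT, belong to EOT, which leaves four at TOC.

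**Mitigations.** SAP 7.4 discloses antibiotic use. The EOT eradication result largely precedes a switch made after EOT. The sponsor reviews data for CE by hand and could remove individual patients. An uninterpretable culture is indeterminate, and that clause could be stretched to cover one taken after rescue. These limit the harm, but none is a scoring rule. A count below 10^3 CFU/mL is interpretable on its face, m-MITT is assigned by program, and the written CE rule keeps rescued failures.

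**Conclusion.** The gap is real and no other section closes it. Followed as written, the plan credits clearances after rescue to ciprofloxacin in the Day 12 eradication rates for ITT, m-MITT, CE-TOC and ME-TOC, in the TOC summaries by key pathogen and ESBL status, and in any microbiologic comparison by ciprofloxacin susceptibility. It also affects the Synopsis's Day 12 microbiologic success, taking success to mean eradication. The primary overall response is untouched.

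The per-patient effect (0.5 points of 200, 2.5 points of 40) follows from the planned numbers. The total does not. It runs from near 0 to 38 points over the assumed rates, and is smaller if some women had cleared before rescue or did not return on Day 12. The direction is certain and the amount unknown. This warrants a written rule before the microbiologic tables are produced; it is not a defect in the primary analysis.

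**What to change.** Add to Protocol 7.2.2 and SAP 5.3 that a culture collected after the start of a rescue antibiotic for uUTI is not counted as eradication. Report it as its own category (rescued before culture), kept in the denominator as not eradicated in both m-MITT and ME-TOC. SAP 4.6 item b would need to admit that category, or these women would drop out of ME-TOC. Show the culture-only rate as a supportive line. A separate category is better than presumed persistence, which would overwrite an observed clear culture in a woman already negative at EOT.

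Where an active antibiotic was given for another reason, score microbiologic response as indeterminate in m-MITT, as overall response already does.

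Cost: SAP wording and one derivation for rescue, since antibiotics for the uUTI are already in the CRF (Protocol 5.4.1). The rule for other antibiotics may need source data, because that section requires no other concomitant medication in the CRF. The eradication rate will be somewhat less favourable, and some women who cleared before rescue will count as not eradicated; the supportive line and the EOT result let the reader see how many.
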